1.2.3. Pembrolizumab known benefits and risks

Pembrolizumab is generally well tolerated over a spectrum of tumour types and demonstrates a favourable safety profile in comparison to chemotherapy. Safety data from over 2700 patients has reported the most common adverse events of all grades were diarrhoea, cough, pruritis, arthralgia, rash, pyrexia and back pain (Pembrolizumab Investigator Brochure, Merck, Sharp & Dohme). Common grade 3-4 drug related adverse events were anaemia, raised alanine aminotransferase and aspartate aminotransferase.

Immune toxicities are well known among the immunotherapy drugs. Immune-mediated adverse reactions of all grades included hypothyroidism (8.4%), hyperthyroidism (3.4%), pneumonitis (3.4%), colitis (1.8%), severe skin reactions (1.4%), hepatitis (0.7%), hypophysitis (0.6%), diabetes mellitus (0.2%) and nephritis (0.1%). Other immune-mediated adverse reactions of clinical significance were reported in less than 1% of patients included uveitis, myositis, Guillian-Barre syndrome and pancreatitis. Events have been reported to occur from as early as the first dose to several months after the last dose of treatment and early recognition can allow initiation of symptomatic treatment preventing delays and discontinuation of treatment. Complications requiring steroids or immunosuppression are commonly reversible.

The first trial to report clinical activity of an immune check point inhibitor in TNBC was a phase 1b trial (KEYNOTE-012) showing that single agent pembrolizumab given at 10mg/kg IV once every 2 weeks (Q2W) was well tolerated and effective[26]. Twenty-seven heavily pre-treated recurrent or metastatic TNBC positive for PD-L1 were treated showing 18.5% of evaluable patients responded with one complete response, 4 partial

responses and 7 stable disease responses. Patients with a LDH greater than twice the upper limit of normal, which represents rapidly progressive disease had no response to pembrolizumab. Three patients remained on pembrolizumab for at least 11 months, which supports previous suggestions of the durability of pembrolizumab. Previous studies have mentioned the use of PD-L1 as a biomarker for response. However this study lacked correlation between the degree of PD-L1 positivity and response, questioning the use of PD-L1 as an appropriate biomarker [26].

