2.2. Secondary Objectives

- To assess time to first positive ctDNA detection from entry into the ctDNA surveillance.
- To assess the rate of detection of overt metastatic disease at the time of first ctDNA detection.
- To assess the median lead-time between ctDNA detection and relapse in the pembrolizumab treatment and observation groups.
- To assess sustained clearance of ctDNA in the observation group.
- Safety and tolerability of pembrolizumab.
- To assess the proportion of patients allocated to receive pembrolizumab who start pembrolizumab.

NB. Secondary objectives relating to the observation group will be evaluated in the patients randomised to the observation group prior to the implementation of protocol v6.0.

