Note: Permanently discontinue pembrolizumab for any severe or grade 3 (grade 2 for pneumonitis) drug-related AE that recurs or any life-threatening event.

- a. Withholding or permanently discontinuing pembrolizumab is at the discretion of the investigator or treating physician.
- b. Renal function can be calculated using Serum creatinine OR estimated GFR (using Cockcroft-Gault).

c. For infusion reactions: if symptoms resolve within one hour of stopping drug infusion, the infusion may be restarted at 50% of the original infusion rate (e.g., from 100 mL/hr to 50 mL/hr). Otherwise dosing will be held until symptoms resolve and the patient should be pre-medicated for the next scheduled dose; Refer to Table 2 – Infusion Treatment Guidelines for further management details.

d. Patients with intolerable or persistent grade 2 drug-related AE may hold pembrolizumab at investigator's discretion. Permanently discontinue pembrolizumab for persistent grade 2 adverse reactions for which pembrolizumab has been on hold for ≥12 weeks.

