18.2. Reporting Adverse Events to ICR-CTSU

Any toxicity, sign or symptom that occurs after commencement of pembrolizumab treatment and within 90 days of the last administration of pembrolizumab, or 30 days following cessation of treatment if the patient initiates new anti-cancer therapy, whichever is earlier, and which is not unequivocally due to recurrence of disease, should be considered an AE.

All AEs must be reported on the relevant CRF and submitted to ICR-CTSU.

The severity of AEs should be graded according to the National Cancer Institute Common Terminology Criteria for Adverse Events (NCI CTCAE) v4.0. For each AE, the highest grade observed since the last visit should be reported.

Abnormal laboratory findings that meet the criteria for grade 2 or above toxicity as defined by NCI CTCAE v4.0 are considered to be clinically significant and should be reported as AEs. Whenever one or more toxicity/sign/symptom corresponds to a disease or a well-defined syndrome only the main disease/syndrome should be reported.

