19.3.2. Secondary Endpoints

Secondary endpoints relating to the observation group will be analysed in the patients randomised to the observation group prior to the implementation of protocol v6.0.

ctDNA surveillance

1) Time to ctDNA detection. This will be calculated as the time from entry into the ctDNA surveillance to first positive ctDNA detection. Statistical techniques for time to event data will be used to summarise data and display the pattern of ctDNA detection graphically.

Therapeutic component

- Detection of overt metastatic disease at the time of first ctDNA detection in patients allocated to pembrolizumab. This will be calculated as the proportion of patients with metastatic disease from CT scan at the same time point as first positive ctDNA detection, and presented with associated exact 95% confidence interval.
- 2) Lead-time between ctDNA detection and recurrence in the pembrolizumab treatment and observation groups. This will be calculated as the time between therapeutic trial entry and first confirmed detection of recurrent disease. Recurrence will include loco-regional and distant recurrence, but will exclude new primary cancers. Statistical techniques for time to event data will be used to summarise data and display time between ctDNA detection and recurrence graphically.
- 3) Absence of detectable ctDNA or disease recurrence after 6 months in the observation group. This will be calculated as the proportion of patients without either detectable ctDNA or disease recurrence 6 months after randomisation to the observation group. Proportions will be presented with associated exact 95% confidence intervals.
- **4)** Safety and tolerability of pembrolizumab in this patient group. Safety will be assessed throughout the treatment period using the NCI CTCAE v4.0 and summarised in tabular format. Reported toxicities

will be coded using Med DRA (current version). The proportion of patients reporting a dose reduction/delay during pembrolizumab will be presented.

5) Commencement of treatment in patients allocated to receive pembrolizumab. This will be calculated as the proportion of patients allocated to receive pembrolizumab who start this therapy. The proportion will be presented with associated exact 95% confidence interval.

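### The safety endpoint in 19.3.2 has a shorter window than the adverse event rules in 18.2, and its one tolerability proportion names dose reduction but omits permanent discontinuation for toxicity

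*Protocol*

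**What the plan says.** Safety and tolerability is a secondary objective with no time limit attached (Protocol 2.2: "Safety and tolerability of pembrolizumab"). The endpoint definition in 19.3.2, therapeutic component item 4, adds one: "Safety will be assessed throughout the treatment period using the NCI CTCAE v4.0 and summarised in tabular format". It then says that toxicities will be MedDRA-coded and names a single tolerability measure: "The proportion of patients reporting a dose reduction/delay during pembrolizumab will be presented".

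Other sections go further in time.

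- Section 18.2 defines an adverse event as "Any toxicity, sign or symptom that occurs after commencement of pembrolizumab treatment and within 90 days of the last administration of pembrolizumab". The limit becomes 30 days after cessation if new anti-cancer therapy begins, whichever comes first. All such events go on the CRF.
- Section 18.3 applies the same window to serious events, and also takes related serious events after 90 days if the investigator learns of them.
- Sections 3.3.1 and 11.4 schedule a safety assessment about 30 days after the last dose.
- Section 1.2.3 says of immune-mediated reactions: "Events have been reported to occur from as early as the first dose to several months after the last dose of treatment". Section 17.12 repeats the point.

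On treatment changes, 17.1 sets a fixed dose, and the table in 17.16 lets pembrolizumab be continued, withheld or permanently discontinued. Several rows give permanent discontinuation at a first grade 3 or 4 event, pneumonitis among them. The note below the table adds: "Permanently discontinue pembrolizumab for any severe or grade 3 (grade 2 for pneumonitis) drug-related AE that recurs or any life-threatening event".

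**The concern.** The definition fits poorly with the rest of the protocol in two ways.

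First, the window. The protocol expects reactions to pembrolizumab after the last dose and collects them. The endpoint that should summarise them stops, on its plain wording, when treatment stops. The gap is proportionally widest in patients who stop early, including those who stop because of toxicity.

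Second, the tolerability proportion. Half of its label, reduction, has no counterpart in the treatment rules. The most serious treatment consequence those rules contain, a permanent stop, is not in it. A reader of the results would normally take this proportion as the summary of how well the drug was tolerated.

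At stake is whether a stated secondary objective is answered completely, in patients who have no visible disease when they start treatment.

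**Working it through.** The safety endpoint has no sample size, target rate or threshold, so there is no plan figure to reproduce. The check compares sections and then gives the scale in time.

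**Step 1: window.**

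| Rule | Section | End of window |
|---|---|---|
| Safety endpoint | 19.3.2, item 4 | End of the treatment period (term not defined) |
| Adverse events | 18.2 | Last dose + 90 days, or cessation + 30 days if new anti-cancer therapy starts |
| Serious adverse events | 18.3 | As 18.2, plus later related events if known |
| Safety visit | 3.3.1, 11.4 | About 30 days after the last dose, or before new therapy |

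The endpoint has the shortest window of the four.

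**Step 2: share of the window after the last dose.** With c cycles of 21 days (11.7), the last dose falls (c − 1) × 21 days after the first. The share after it is 90 / ((c − 1) × 21 + 90).

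- c = 17, the last cycle in the schedule: 90 / (336 + 90) = 90/426 = 21%.
- c = 4: 90 / (63 + 90) = 90/153 = 59%.

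If the treatment period is taken to run to 21 days after the last dose, 69 days remain outside: 69/426 = 16% and 69/153 = 45%.

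If new anti-cancer therapy starts within the window, and cessation is taken as the day of the last dose, the window ends at 30 days: 30 / (336 + 30) = 8% and 30 / (63 + 30) = 32%.

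All of these are shares of time. The protocol gives no rate of events by time since last dose, so they cannot be turned into shares of events.

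**Step 3: tolerability proportion against the actions in section 17.**

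| Action | In section 17? | In the 19.3.2 proportion? |
|---|---|---|
| Dose reduced | No (only the infusion rate can be lowered, 17.7) | Yes |
| Dose withheld or delayed | Yes | Yes, as delay |
| Permanently discontinued | Yes | No |

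Take a patient with a first grade 3 pneumonitis, for whom 17.16 gives permanent discontinuation. No dose was reduced and none need have been delayed, so the patient need not enter the numerator. The pneumonitis itself is graded by CTCAE, coded and tabulated.

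**Step 4: illustrative counts.** The protocol states no discontinuation rate. Under assumed rates of 5%, 10% and 20%, the 30 pembrolizumab patients of the main scenario in 19.1.2 would include 30 × 0.05 = 1.5, 30 × 0.10 = 3 and 30 × 0.20 = 6 stops for toxicity. The stated proportion would not show any of them as stops.

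**The case against.** The strongest reply is that this is loose wording with no practical effect. Item 4 contains no exclusion rule, the treatment period is nowhere defined, and the sentence on coding reported toxicities has no time limit. Section 19.4 defers further detail to the statistical analysis plan, which is not shown and could tabulate the full collection window and list discontinuations. An empty reduction category adds nothing to the proportion and biases nothing.

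Part of this stands. The reduction wording is harmless in itself. A missing table row alone would be a matter for the analysis plan. But the protocol does not leave the window or the measure open: it states both, and the stated window disagrees with 18.2. An analysis plan that used the full window would be departing from the endpoint as written.

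A reader might go further, and the documents do not support these inferences:

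- **That late events are lost.** They are collected under 18.2 and 18.3, and the committee's safety review in 19.5 is not confined to treatment. The defect is in the definition of the endpoint, not in data capture.
- **That a patient stopped for toxicity is classed as having tolerated treatment.** No such category exists, and an on-treatment reaction still appears in the toxicity table.
- **That the benefit-risk conclusion is biased towards the drug.** The omissions can only make the summary look more favourable, but safety is descriptive here, with no comparator or decision rule, and the size is unknown.
- **That the reaction rates in 1.2.3 can be summed to give a number of uncounted stops.** They are all-grade rates, several rows of 17.16 respond to lower grades by withholding, and the hepatitis row says withhold for grades 2 to 4.

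**Conclusion.** The point holds as an internal inconsistency in a stated secondary endpoint. On its plain wording, 19.3.2 analyses safety over a shorter period than 18.2 collects it, in a protocol that twice says reactions can appear months after the last dose. Its one tolerability proportion names an action the protocol does not provide for and omits one that it does.

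The excluded part of the 90-day window is about 21% of its length after a full course and 59% after 4 cycles, counted from the last dose. It is smaller if the treatment period is read as including the final cycle or if new anti-cancer therapy shortens the window. How many events or stops would go unreported cannot be derived from the protocol. The conclusion assumes only that the treatment period means what it ordinarily means. The change is worth making because it is cheap and removes a contradiction; no bias of known size has been shown.

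**What to change.** Reword 19.3.2, item 4:

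1. Define the safety analysis window as the adverse event window of 18.2: first dose to 90 days after the last dose, or 30 days after cessation if new anti-cancer therapy starts, whichever is earlier. Show events after the last dose separately as well as within the total.
2. Replace the single tolerability proportion with two: patients with a dose withheld or delayed, and patients permanently discontinued for toxicity. Remove the reference to reduction.

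This concerns analysis and reporting only and leaves every treatment rule as it is. The cost is a wording change and a few table rows. The adverse event data are already required on the CRF. The CRF is not shown, so it should be confirmed that toxicity is recorded as a reason for stopping (11.6 lists it as one). The downside is slightly less favourable reported toxicity.

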19.3.3. Exploratory Endpoints

Exploratory endpoints relating to the observation group will be analysed in the patients randomised to the observation group prior to the implementation of protocol v6.0.

- 1) Descriptive differences in time between ctDNA detection and disease recurrence, and disease free survival, between patients in the pembrolizumab treatment and observation groups. The times from first ctDNA detection to disease recurrence, and to disease free survival event (i.e. including new breast primary cancer or breast cancer death) will be calculated using statistical techniques for time to event data and summarised for each randomised treatment group. This will be calculated and presented separately for the pembrolizumab and observation randomised groups, with patients included in their randomised group regardless of treatment actually received. If recurrence is confirmed after initial continuation of treatment for development of isolated lymphadenopathy, the date of first scan will be used in analyses as date of recurrence.
- 2) To explore predictors of sustained ctDNA clearance on pembrolizumab. The proportion of patients with absence of detectable ctDNA or disease recurrence 12 months after commencing pembrolizumab will be tabulated by clinical and biological factors of interest. Consideration will be given to the use of logistic regression to investigate relationships between factors considered and ctDNA clearance in univariate and multivariable models.
- 3) To explore potential predictors of relapse and ctDNA detection, and alternative definitions of ctDNA clearance. Lead time will be calculated as described previously. Statistical techniques for time to event data will be used to summarise lead time data and display graphical according to clinical and biological factors of interest. Alternative definitions of the proportion of patients without either detectable ctDNA or disease recurrence at 12 months, and other time points, after randomisation to the observation group. Proportions will be presented with associated exact 95% confidence intervals.
- 4) Association between ctDNA clearance and time to recurrence in the pembrolizumab group. The times from first ctDNA detection to recurrence event will be calculated using statistical techniques for time to event data and summarised separately for patients with and without sustained ctDNA clearance. If numbers allow, time to recurrence will be formally compared between those with and without ctDNA clearance using standard time to event methods.

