2.3. Exploratory Objectives

- To explore differences in time between ctDNA detection and disease relapse, and disease free survival, between patients in the pembrolizumab and the observation groups.
- To explore predictors of sustained ctDNA clearance on pembrolizumab.
- To explore potential predictors of relapse and ctDNA detection, and alternative definitions of ctDNA clearance.
- To assess the association between ctDNA clearance and time to recurrence in the pembrolizumab group.

NB. Exploratory objectives relating to the observation group will be evaluated in the patients randomised to the observation group prior to the implementation of protocol v6.0.

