19. STATISTICAL CONSIDERATIONS

19.1. Statistical design and sample size justification

19.1.1. Screening component

This consists of a single cohort who will have ctDNA surveillance every 3 months for 2 years. Patients who are found to be ctDNA positive within the first 12 months of ctDNA surveillance will enter the therapeutic trial. The size of the screening cohort has been chosen to anticipate the required number of patients eligible for the therapeutic trial (assuming 30% patients have a positive ctDNA during the first 12 months) and will provide further descriptive information relating to ctDNA incidence and lead time over detection of overt clinical relapse. The trial aims to recruit 150 patients into ctDNA surveillance. It is anticipated that approximately 75% of patients initially enrolled will be eligible for ctDNA surveillance, therefore approximately 200 patients will be recruited in total. The Independent Data Monitoring Committee (IDMC) will monitor the ctDNA positivity rate observed throughout the course of the trial and make recommendations regarding any increase or decrease in the overall size of the screening cohort based on this. All patients who enter the screening cohort will have the opportunity to enter the intervention phase if they become ctDNA positive within the first 12 months, regardless of the overall number of patients currently recruited to the therapeutic component of the trial.

If the incidence assumptions are correct and approximately 30% of patients have a positive ctDNA during the first 12 months of surveillance then 150 patients will enable the incidence of ctDNA positivity to be estimated with a two-sided 95% confidence interval of +/-7.3%.

In the original randomised trial design (prior to the implementation of protocol v6.0) the planned exploratory analyses were detailed as follows: Exploratory analysis will be performed comparing time to macroscopic relapse between two groups, 1) patients who remain ctDNA negative within the first 12 months and do not enter the therapeutic trial, and 2) patients who become ctDNA positive and are randomised to the observation group in therapeutic trial.

Subsequent to the removal of the randomised component (implementation of protocol v6.0) the above analyses will be amended to censor any patient who had been previously randomised to the observation group at the date they subsequently started pembrolizumab.

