Under the original randomised study design (prior to protocol v6.0), of 150 patients screened, approximately 70% will remain ctDNA negative and 10% will be allocated to the observation group in the therapeutic trial (with the remaining 20% allocated to pembrolizumab in the therapeutic trial). Therefore assuming a 7:1 allocation ratio between groups 1) and 2) described above, a hazard ratio of 3.02 (assuming a reduction in 2 year relapse free rate from 80% to 51%) can be detected with 80% power, alpha 5% (two sided). We note that the HR demonstrated in retrospective testing for the ctDNA assay was 13.6, and the trial will be well powered for prospective validation.

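### Exploratory endpoint 3 seeks predictors of relapse and of ctDNA detection, but the only outcome it names for them is lead time, which exists only in patients already ctDNA positive

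*Protocol*

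**What the plan says.** The exploratory objective in Protocol section 2.3 is "To explore potential predictors of relapse and ctDNA detection, and alternative definitions of ctDNA clearance". Section 19.3.3, item 3, repeats it and then describes the analysis. For the two predictor aims it says "Lead time will be calculated as described previously" and that time-to-event methods "will be used to summarise lead time data and display graphical according to clinical and biological factors of interest". The rest of the item concerns alternative definitions of clearance.

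The earlier description of lead time is in section 19.3.2, therapeutic component, item 2. The endpoint is "Lead-time between ctDNA detection and recurrence in the pembrolizumab treatment and observation groups", and the derivation reads "This will be calculated as the time between therapeutic trial entry and first confirmed detection of recurrent disease".

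Section 19.1.1 describes one of its comparison groups as "patients who remain ctDNA negative within the first 12 months and do not enter the therapeutic trial" and expects, under the original randomised design, that "approximately 70% will remain ctDNA negative".

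Section 19.3.2 also has a surveillance endpoint, time to ctDNA detection: "This will be calculated as the time from entry into the ctDNA surveillance to first positive ctDNA detection". No analysis by clinical or biological factor is attached to it.

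**The concern.** The aim and the outcome do not match. A predictor of detection has to be sought where some patients are detected and others are not. A predictor of relapse in the surveillance cohort has to be sought among all patients at risk of relapse. Lead time is conditional on detection, so it offers neither setting. A factor that acts on whether ctDNA appears, and not on what follows, leaves no trace in it. A factor associated with shorter lead time is a predictor of faster relapse after detection, in patients mostly allocated pembrolizumab. That is a different quantity from risk of relapse after standard treatment.

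At stake is whether this exploratory endpoint can deliver what section 2.3 promises. A SAP that follows item 3 faithfully would carry the mismatch forward.

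**Working it through.** **1. Who has a lead time.** Section 19.3.2 starts the clock at therapeutic trial entry. Under section 19.1.1, patients who stay negative through the first 12 months never enter the therapeutic trial, so they have no time origin. Samples from the second year are exploratory and not analysed in real time (section 3.1). A first positive in that year therefore normally gives no lead time either, except where active surveillance was extended because of the COVID-19 suspension.

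**2. The protocol's own figures, reproduced (section 19.1.1).** Inputs: 150 patients in surveillance; 30% positive in the first 12 months; original split 70% negative, 10% observation, 20% pembrolizumab; two-year relapse-free rates of 80% (negative) and 51% (positive, observation).
- Precision of the positivity rate: 1.96 × √(0.3 × 0.7 / 150) = 7.3%, as stated.
- Detectable hazard ratio: ln(0.51) / ln(0.80) = 3.02, as stated.
- Events needed by Freedman's formula, with allocation ratio φ = 1/7 and HR = 3.0175: (1.96 + 0.84)² × (1 + φHR)² / [φ(1 − HR)²] = 27.6. Events expected: 105 × 0.20 + 15 × 0.49 = 28.35. The stated 80% power is consistent with this formula.

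The inputs are therefore read as the protocol meant them.

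**3. Patients in and out of item 3.**
- With a lead time: 0.30 × 150 = 45.
- Without: 0.70 × 150 = 105.

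Removing randomisation in v6.0 changes the division of the 45 between groups, not the 45 v 105 split.

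**4. Predictors of detection.** In the surveillance cohort the contrast is about 45 detected v 105 not detected in year 1. In the lead-time set it is 45 v 0. Detection does not vary, so no model can estimate an association with it.

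An illustration with assumed rates: 200,000 simulated patients; a binary factor raises detection from 20% to 40%; time from detection to relapse is exponential with median 7.1 months (the lead time cited in section 1.1) and does not depend on the factor. Median lead time was 7.2 months in both groups. A factor that doubles detection is invisible in lead time.

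**5. Relapses outside item 3.** At the 80% relapse-free rate, 105 × 0.20 = 21 relapses by two years. Their share of all relapses depends on rates that the protocol does not fix. The table varies the two-year relapse rate in the 105 (5%, 10%, or the protocol's 20%) and in the 45 (the protocol's untreated 49% applied to all of them, or 100%).

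| Relapse rate in the 105 | Relapses in the 105 | Share left out if 49% of the 45 relapse (22.05) | Share left out if all 45 relapse (45) |
|---|---|---|---|
| 5% | 5.25 | 5.25 / 27.3 = 19% | 5.25 / 50.25 = 10% |
| 10% | 10.5 | 10.5 / 32.55 = 32% | 10.5 / 55.5 = 19% |
| 20% | 21 | 21 / 43.05 = 49% | 21 / 66 = 32% |

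The range is about 10% to 49%.

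**The case against.** The strongest reply is that item 3 is a loose sketch of an exploratory analysis. It never says that lead time is the only outcome, and section 19.4 leaves further detail of methods to a SAP. A suitable outcome for detection already exists as a secondary endpoint, and sections 26.1.2 and 26.1.3 allow for optional biomarker work on relapse and detection without tying it to lead time. Lead time by factor is also a fair question in its own right: section 26.1.1 plans time from detection to recurrence by PD-L1 expression.

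Much of this stands. The repair is one of wording, and lead time by factor is worth keeping. It does not remove the mismatch. The protocol has not left the outcome open; it names one, and that one cannot serve the stated aim. Nothing elsewhere attaches clinical or biological factors to time to detection or to relapse in the whole cohort, and the optional work in section 26 names no outcome.

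Three stronger readings are tempting and are not supported:
- A reader might infer that the protocol ignores relapses in ctDNA-negative patients altogether. It does not. Section 19.1.1 compares time to macroscopic relapse between patients negative in the first 12 months and those randomised to observation. That is a comparison by ctDNA status only.
- A reader might infer that conditioning on detection would hide or reverse real risk factors for relapse. The illustration shows only that a predictor of detection goes unseen; reversal has not been shown.
- A reader might take 21 relapses as an estimate. It rests on a rate assumed for a power calculation. Some of the 105 may also turn positive in year 2 before relapse, so not all would be ctDNA negative at relapse.

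**Conclusion.** The point holds for exploratory endpoint 3. The outcome it names cannot show any predictor of ctDNA detection; this follows from the definition and does not depend on sample size or assumed rates. For relapse, it addresses only time to relapse after detection.

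On the planning figures about 45 of 150 patients contribute and about 105 do not. About 21 relapses fall outside the endpoint if the 80% relapse-free rate is right, or 10% to 49% of all relapses over the rates examined.

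The consequence is limited. This is part of one of four exploratory endpoints, and no success criterion, sample size or primary conclusion depends on it. It should be corrected because the stated aim is otherwise unmet and the correction is cheap.

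**What to change.** Amend section 19.3.3, item 3, to name an outcome and a cohort for each aim:
- **Predictors of detection:** time from surveillance entry to first positive ctDNA (the existing secondary endpoint), by clinical and biological factor, in all patients entering surveillance.
- **Predictors of relapse:** time from surveillance entry to recurrence, by factor, in the same cohort and regardless of pembrolizumab. Add a sensitivity analysis with pembrolizumab start as a time-dependent covariate. Do not rely on censoring at pembrolizumab start: a positive ctDNA result triggers that treatment, so the censoring would be informative and would remove follow-up from the patients at highest risk.
- **Lead time by factor:** keep it, labelled as a description of time to relapse after detection in ctDNA-positive patients.

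The cost is a few sentences and a little extra analysis. Serial ctDNA results and recurrence follow-up are already collected across the surveillance cohort (sections 3.3.2, 8.1.3 and 8.2), so no new data are needed.
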